**REVISION HISTORY**

Revision #	Version Date	Summary of Changes
1	09/03/2020	Updated honorarium to \$25
2	10/19/2020	Clarifies that only Aim 2 involves human subject research Reduces number of participants in focus groups Clarifies number of focus groups versus interviews
3	07/29/2021	Updates methods of Recruitment using Emory On-Hold Services, Social Media.

## 1. Study Summary

Study Title	Mastering the Challenges of Dementia Family Caregiving in a Time of COVID-19: An Online Course
Study Design	Two group waitlist control design
Primary Objective	Develop a prototype pandemic caregiver training and education course
Secondary Objective(s)	Conduct a waitlist-control design test of the prototype course
Research Intervention(s)/Interactions	Self-paced asynchronous online course
Study Population	Dementia Family Caregivers
Sample Size	100
Study Duration for individual participants	24 weeks
Study Specific Abbreviations/ Definitions	COVID-19: Coronavirus Disease 2019 PLWD: Person living with dementia CES-D: Center for Epidemiological Studies-Depression RMBPC: Revised Memory and Behavior Problems Checklist MPI: Multiple principal investigator
Funding Source (if any)	National Institute on Aging (pending)

## 2. Objectives

Aim 1: Develop a prototype pandemic caregiver training and education course. Through iterative Design Studio sessions with dementia family caregivers, program faculty, COVID-19 specialists, and other clinical experts, we will design a competency-based course curriculum that applies a psychoeducation framework to the design. Based on this process, we will storyboard and script a course with 30-35 brief video- and text-based instructional modules. After final revisions, we will produce the instructional text and videos and finalize the self-paced course to be tested in Aim 2 activities. Aim 1 activities do not constitute human subject research; they are intended solely to gather input from a variety of perspectives, including from individuals similar to those with whom the eventual program will be tested, to assist in program design.

Aim 2: Conduct a waitlist-control design test of the prototype course. We will identify a diverse set of dementia family caregivers (N=100; 1/4 African American) whom we will ask to enroll in the course to participate in formative and summative research related to it. The test will gather information about the usability and salience of the course as well as its preliminary efficacy. The course faculty and research team's observation of participants' responses to the course and the

embedded interactive exercises and the results of semi-structured interviews with a subsample of 20 participants will enable us to further refine the course.

### **3. Background**

Family caregivers, the backbone of care for the upwards of 7 million community-dwelling individuals living with Alzheimer's disease in the U.S., provide at least 85% of the care these individuals receive, at some risk to their own well-being, and are instrumental in navigating healthcare systems. Without their care, it is almost certain that PLWD would have much higher rates of acute and emergency care use than their age-matched peers, perilous venues for them in the best of times, potentially deadly during this pandemic. With COVID-19 restrictions, the amount of care they provide and the expertise needed to provide the care will increase. Typically, caregivers are strangers in healthcare and pandemic landscapes, but they are now called on to enact home care and safety measures and navigate an intricate, complex, and opaque system without the benefit of a compass or a translator – and largely without understanding their role in or having the skills for navigating the system. A variety of interventions, including our own, have demonstrated benefit in enhancing caregivers' caregiving capacities, with resulting positive outcomes for both caregivers and care recipients. Only a few of these useful interventions, Tele-Savvy among them, have employed distance delivery means, thus enabling rural caregivers and others precluded by circumstance from attending in-person programs to take part in the intervention programs.

Early findings from the synchronous/asynchronous online three-arm randomized Tele-Savvy trial provide encouraging support for this project. The online Tele-Savvy psychoeducational caregiving course we propose appears to work and caregivers do fully participate in its asynchronous component. We used multilevel mixed models to test for group, time, and group-by-time effects for each of the outcomes. Results from the first 220 participants in the baseline to six-month segment of this three-arm trial indicate that Tele-Savvy participants had statistically significant group-by-time reductions in depression and strain and statistically significant group-by-time increases in caregiver mastery, compared to those in the other two study arms. We found a significant group-by-time effect on CES-D-assessed caregiver depression ( $p<.001$ ) with the active group showing significant decreases over time ( $p<.001$ ). We found a significant group-by-time effect on caregiver perceived strain ( $p<.001$ ) with the active group demonstrating significant reductions over time ( $p<.001$ ) and the waitlist control group demonstrating significant increases ( $p=.010$ ). Likewise, there was a significant group-by-time effect ( $p=.001$ ) on caregivers' reactions to care recipient behaviors (RMBPC) with significant reductions over time among the active caregivers ( $p=.001$ ). Caregiver competence likewise demonstrated a significant group-by-time effect ( $p=.009$ ), with the active group demonstrating significant increases over time ( $p<.001$ ). Findings regarding caregivers' mastery were comparable: a significant group-by-time effect ( $p=.003$ ) with the active group demonstrating significant increases over time

(p<.001). Canvas-based analytics indicate that participants were highly adherent in viewing the 36 asynchronous 8-15 minute daily video lessons, spending, on average, more than 8 hours watching the videos over the course of the 43-day program.

Much of the “normal work” of caregiving involves guiding PLWD through days at home and in the community that are as calm, engaging, and event-free as possible, and that has been the mastery-development focus of much of MPI [name]’s work. The COVID-19 pandemic, however, brings into stark focus caregivers’ need to acquire the knowledge, skills, and competence to maintain care recipients’ safety and ensure their safe navigation of the healthcare system. Functioning as a public health/infection control expert and healthcare system navigator requires skills and knowledge that family members do not possess as a matter of course.

#### **4. Study Endpoints**

The key study outcomes are measures of caregiver psychological well-being and confidence in their ability to provide effective care to the PLWD. The study ends after participants complete the online course and the follow-up interviews conducted to gather these study endpoints/outcomes .

#### **5. Study Intervention / Design**

The proposed study is a two-group waitlist control design to study a psychoeducational intervention for dementia caregivers. The study has two phases: 1) course development and 2) testing.

Our overall approach to course development and testing is one that we have used successfully in MPI [name]’s work to produce video instructional content for dementia family caregivers. End-users are engaged throughout in both developing the broad outlines of an instructional curriculum, crafting the granular elements of the curriculum (e.g., text and video content for individual lessons), and providing formative feedback on the prototype product. The approach to co-production of care that informs the sense of mastery to be developed is one that MPI [name] has successfully deployed in MPI [name]’s Integrated Memory Care Clinic (IMCC), Emory’s patient-centered medical home for PLWD.

#### **6. Procedures Involved**

Aim 1 [Weeks 0-24]. Table 1 below outlines the activities in which we will engage to stand up the caregiver education course we will test in Aim 2. Guided by a Design Studio process, we will engage in an iterative process of curriculum development, course design, and materials production that will involve a diverse group of dementia family caregivers, our core pilot project team, other clinical and caregiver experts, and our educational design consultant. The Design Studio’s process is deeply grounded in the early and frequent involvement of potential end users in product design and uses a variety of brainstorming techniques to challenge and refine an emerging product – like

this course. This process it will play an important role in developing the Aim 1 prototype pandemic caregiving course. This is a design, not a research, activity.

The Design Studio activities will be conducted in three stages using focus group methods. To facilitate group discussion by all participants, the sample size for each Design Studio session will be limited to 8-10 participants per group, an average of nine per group. Drs. [name] and [name] (co-Investigators) will lead these discussions with one acting as moderator and the other as trained observer. The observer will assist with the process and record observations of participants' nonverbal interactions and behaviors. Design Studio sessions will last approximately 60-90 minutes and be audio-recorded and transcribed verbatim.

**Table 1. Activities to be Undertaken in Aim 1**

Aim 1 Activities	Project Weeks						
	0	4	8	12	16	20	24
• Project team develops preliminary course content table	----	x					
• In collaboration with educational consultant, develop preliminary course design		-----	x				
• Design Studio #1,		-----	x				
• Course content and design revisions (team and educational consultants) some scripting			-----	x			
• Design Studio #2,			-----	x			
• Course revisions, storyboarding, video scripting continues				-----	x		
• Design Studio #3,					-----	x	
• Finalization, including scripting, video production, placement on Canvas platform						-----	x
• Aim 2 recruitment and consenting begins							-----

Table 2 below represents the broad initial draft outline of the key sections and up to 36 specific topics we believe to be essential segments in the course. The outline will serve as the basis for course design activities with our instructional designers and specialists, and these together – the topic outline and rough course design – will provide the material for our first Design Studio exercise. We emphasize the draft nature of this outline. The Design Studio process emphasizes empathy with the end-user experience as the driver of end-product design. We will use the empathize/define phases of design thinking to understand how generally to design the course and associated elements and use ideation/prototyping techniques to clarify what should be included or not included in more detail. Constructed as it has been from an "expert" perspective, the draft document likely omits significant elements of and perspectives on caregiver mastery development that will need to be incorporated into the eventual design of the proposed course.

In the first audio-recorded Design Studio exercise, to be held online if necessary, we will engage IMCC Advisors and a diverse group of other caregivers in an initial exploration of the overall objectives and the preliminary form and content of the course. After the first group, the team, led by investigators [name] and [name], will analyze the transcripts, using a thematic analysis approach, an iterative process that will involve deconstructing text, identifying salient themes, conceptualizing relationships, and synthesizing results. Two primary coders ([name] and [name]) will independently code the first transcript. A

secondary coder ([name]) will review the coding and reconcile any differences. Codes will be discussed among the entire project team to ensure concordance and reliability. This analysis will guide refinements of the course and course materials as well as development of draft text and video scripts for two topic segments.

**Table 2. Preliminary Draft of COVID-19 Course Curriculum Content**

Key Sections	Topics Within Sections	
Introduction	Caregiving as Skilled Work	Caregiver: Co-producer of Care
Caregiving for a Person Living with a Dementia Disorder during a Pandemic (COVID-19)	COVID-19: An introduction	Infection Control 101
	Hand washing and sanitizing	Masks and gloves? Really? When?
	When guests/workers enter the home	Going out and coming back in
	The threats of sheltering in place: isolation	Falls Prevention – avoiding the ER
	Longer days of caregiving	Care when person is in other settings
	Quality of life: threats and choices	What's the plan for the person's care?
	A crisis plan: What if you become ill?	Reliable Information, Fake News, and Scams
Navigating the Health Care System for a Person Living with a Dementia Disorder	How providers hear you	SBAR – Talk like a nurse
	Asserting your standing in the case	Prepping for telemed/out-patient visits
	Safe Use of the Emergency Department	Packing for an emergency
	When the person is hospitalized	Coordinating input from multiple providers
	Transferring back home	How to best use home care
	Getting jargon translated	Case Management: think like a Social Worker
Guiding and Managing Daily Life	The “clinical role” of the caregiver	Designing engaging tasks and activities
	Think and process like a Nurse	Care of chronic conditions
	Caregiver self-care	Using other resources

These materials will serve as the stimuli for the next audio-recorded Design Studio convened with IMCC caregiver Advisors, other caregivers, and also clinicians and Roybal Center Advisors. In this session, the revised outline will be subject to group scrutiny and suggestions. Again, team analysis of the results of the exercise will address key development questions:

- What's missing?
- Where is emphasis needed?
- What's irrelevant?
- What is/are key takeaway lesson(s)?
- Do educational methods encourage involvement and promote the specific caregiving mastery at which we are aiming?

Following analysis comparable to that employed after the first Design Studio session, we will produce a near-final course design, attending to issues of the “feel” and readability of the course, the exercises and opportunities for interactivity to be included, and the methods by which the instructor will monitor and provide feedback. We will also develop penultimate versions of course text and video asset scripts and begin production of caregiver and instructor manuals and other course materials.

These materials will provide the grist for the third Design Studio exercise, again an audio-recorded session convened primarily with caregiver participants but with some clinical and educational expert participation. We ask the same “What do you think?” questions about the content, structure, format, and mode of delivery of the course and

the proposed instructional videos (e.g., Is a lecture format acceptable? Should there be a combination of graphics and voiceover? Would some kind of embedded enactment be useful? What exercises might prompt interaction and foster mastery?).

Following an analysis comparable to those described above, the team will go into full production mode. We will work with the School of Nursing instructional design team to finalize scripting for the possibly as many as 36 segments, finalize the look, feel, and flow of the course, embed it on Canvas, a cloud-based learning management platform used by our School of Nursing, and move to the production of an accompanying caregiver manual and other associated course materials. The team will shoot the video assets – likely small (4-8 minute) mini-talks provided by our team and other experts – that will introduce and reinforce the text and pictorial content of the course. Based on previous experience, video production should take no more than 3-5 days, then editing and integrating these materials into the final course should take no more than three weeks.

**Aim 2 [Weeks 16-52].** Drawing on the recruitment resources identified above, we will recruit 100 caregivers in two waves of 50 each to participate in a waitlist-control design pilot test. When 50 individuals are identified for the first wave, we will contact them, obtain their consent for participation, and, using established instruments delineated in Table 3 below to assess depression, anxiety, burden, and mastery, gather, through 30-minute phone or video interviews, baseline quantitative data on mood and caregiving competency. Once all participants in each wave have completed their baseline quantitative interviews, we will randomly assign half (25) to immediately enroll in and begin the course; we will inform the other half of the group (25) that the course will be open for their enrollment after a waiting period of approximately eight weeks, the time it will take the immediate participants to complete the course. All participants will again be interviewed at that 8-week point, following the immediate group's course completion and prior to the wait-list group's enrollment. All will be interviewed again 8 weeks later. This same pattern of data collection and random assignment will be followed with the second wave participants.

**Table 3. Scales to be Used in Qualitative Interviews**

Outcome Domains/Scales	Description of Validated Scales
The CES-Depression Scale 	21-item self-report depression scale
Stait-Trait Anxiety Inventory 	20-item self-report scale of positive and negative anxiety experiences
Perceived Stress 	16-item scale of self-reported caregiving stress
Revised Memory and Behavior Problem Checklist (RMBPC) 	24-item scale reporting on frequency of disturbing care recipient behaviors and severity or caregiver reactions to these behaviors.
Zarit Burden Scale 	22-item scale of objective and subjective caregiver burden
Caregiver Mastery Scales 	3 3-5 item scales of caregiver mastery of caregiving situations
Caregiver Competency Self-Assessment 	18-item caregiver self-assessment of perceived capacity to manage care situations

The Aim 2 baseline, midpoint, and final instrument-based interviews for all participants and audio-recorded semi-structured follow-up formative evaluation interviews with selected participants will be conducted by phone or videoconference by an interviewer trained and supervised by Co-Investigator [name]; a protocol used in [name]'s Tele-Savvy study will be employed to identify and respond to indications of extreme caregiver stress. Focus groups (Aim 1) will be conducted online, led by [name] and [name].

Three sources of information will enable us to move forward with the preparation of a revised course. The interactive elements of the course (discussion board, exercises and reflections) and the course instructor's observations will enable us to gauge caregivers' understanding of, reactions to, and apparent benefit from individual segments of the course. The Canvas platform allows us to monitor caregivers' course behaviors (e.g., time spent on segments, repeated viewing of segments, extent of participation in interactive components). This information may point to the relative importance of segments as well as the usability of interactive components. The post-course qualitative interviews with caregivers will provide extensive information about topic matter and the usability and acceptability of course material and overall course design. Data from these sources will begin to flow from the point of the gathering of baseline data from the first wave of participants (approximately week 22) and will continue through the qualitative interviews with course participants (approximately week 48). MPI [name] will lead the team's efforts to distill these data strands into practical course revision design activities with the instructional design consultant team to map the steps needed to produce a final course version by project's end.

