## **10. Subject Population**

We will seek to enroll family members (or friends) who self-identify as a principal caregiver and the principal companion of a community-dwelling PLWD during healthcare encounters. We will provide verbal and written instructions in how to access and use the course, provide a schedule for their completion of the course over the next 6-8 weeks, and mail out course materials. At the end point of each wave, we will purposively select 10 caregivers to participate in semi-structured interviews (total n=20) based on varying caregiver characteristics and findings from baseline quantitative data (e.g., stress levels, gender, race/ethnicity). Interviews will last approximately 45 minutes and will ask questions about the overall contribution of the course to their own perceived sense of competence as caregivers and healthcare navigators during the pandemic. We will also seek their responses to the course (Acceptable? Usable? Relevant? Enough? Too much? What's missing? How to improve?). We will provide \$25 gift cards for participation in each baseline focus group and post-intervention semi-structured interview.

Caregivers would be excluded if their loved one is institutionalized or receiving hospice services or there are plans to do so within the next three months. Participants must also be able to read and speak English and be able to access the online course materials.

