### Payments to Participants

We will provide \$25.00 gift cards (e.g., Visa cards) to participants for each interview in which they take part. All trial participants will be asked to take part in a baseline interview and then subsequent interviews 3 and 5 months later. About 20% will be asked to take part in focus groups prior to their enrollment in the course, and about 20% will be asked to take part in semi-structured interviews following course completion. Thus, the maximum payment for any participant would be \$100.00

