## **15. Risks to Participants**

We believe that caregivers taking part in the trial of the Caregiving During Crisis program will be exposed to very low risks. The two main risks are of transient emotional distress and breach of confidentiality. These are described below.

Transient emotional distress. As persons providing care to a person living with dementia and doing so under the strains of the threat and restrictions of a pandemic, subjects in this study are already very likely to be experiencing a higher than normal level of stress and distress. The content of the course will draw their attention to their situation in ways that might make them more acutely aware of their distress or cause them to lower the defenses they might have

erected to fend off the distress. Likewise, the subject matter raised and the questions posed in the research interviews, the focus groups, and semi-structured interviews may also call attention to distressing matters and situations.

Based on our research experience with similar study subjects and the same questions and methods, we judge the occurrence of such distress to be relatively infrequent (perhaps in 25% of cases), of low magnitude (perhaps a 2 on a scale of 10, where 10 is the highest), of very brief duration, and fully reversible. The research interviewer will be trained to recognize such events and to provide ways to back away from and calm them. The participating investigators who would conduct the focus groups or semi-structured interviews are experienced in working with dementia caregivers and in managing such transient events in ways that permit the caregiver to work through them in a brief, respectful, and calming manner.

We can see no procedures in the study that might produce currently unforeseeable risks, and we can see no procedures that might put others at risk who are not in the study.

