## **18. Provisions to Protect the Privacy Interests of Participants and Confidentiality of Participants' identifiable data**

### Protection of Privacy Interests.

There are very few threats to participants' privacy interests involved in the study, and below we describe how we will minimize and manage those threats:

- Except in the focus groups in which we will ask 20% of subjects to take part, there is no direct contact between and among study subjects. Participation in these focus groups is entirely voluntary; no identification is provided about participants to other participants, and participants can choose to take part without video.
- The only personal information to be obtained will be gathered in baseline interviews; we have described above the measures we will take to remove identifiers from the data stored in REDCap
- The research interviewer will be trained by investigator [name] in techniques designed to make participants feel at ease with the questions being asked in the research interviews. Training will involve simulated research interviews conducted with project investigators by the research interviewer in which the interviewer will be expected to react effectively to situations in which the interviewee exhibits signs of feeling discomforted or intruded upon.
- The focus groups and semi-structured interviews will be conducted by study investigators, all of whom are experienced in interacting with caregivers and helping them to feel at ease in situations that might feel intrusive or distressing.

The only member of the research team who will have access to sources of private information about the participants will be PI [name]; no other team member will have or be granted access to that information.

As noted above in #15, all confidential data will be separated from REDCap files and transcripts, all of which will use ID numbers, and the confidential material will be stored

separately in PI [name]'s Emory encrypted computer. None of the data from the study will be entered into participant's medical records.

We will follow NIH policies in retaining and destroying identified study information. Audio-recordings will be destroyed at study's end.

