## **22. Resources Available**

The research is being conducted as an administrative supplement to Emory's Roybal Center for Caregiving Mastery; as such, it will have administrative support through the Center. It is, as described above, also being conducted within the context of the study team members' several involvements in local, state, and national engagements, all of which are directly related to issues of dementia care and the support and development of the capacity of family caregivers to provide effective care to community-dwelling persons living with Alzheimer's disease and related disorders.

Recruitment of 100 study participants seems very feasible. Within the immediate reach of the study team there are at least 1,000 eligible caregivers, and our extended reach, especially through the NIA-supported network of Alzheimer's Disease Centers (with a number of which we have worked closely) there are many thousands more.

The administrative supplement adds effort in the Roybal Center to both investigators [name] and [name], and it provides time for investigator [name].

All study personnel are currently working from home, but in a phase 3 or 4 relaxation of restrictions situation, the Center has designated space in the School of Nursing, and all investigators have private offices and Emory encrypted computers. Under both scenarios, the facilities are appropriate for conducting this fully online study.

We have described above the measures we will take to ensure that any transient emotional distress participants might experience can and will be handled at the time of occurrence, and we do not foresee the need for any additional psychological resources. The study does not involve procedures that might require medical resources.

This is a small study with only an interviewer and Center Program Manager involved beyond the investigators. The procedure for training the interviewer was described above. The PI will train the Program in the conduct of the Eligibility procedure and the Consent Call, should she be the team member to handle either or both of these.

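### Section 6 conflicts with Sections 15 and 18 on who runs the course-feedback interviews, and, separately, nothing keeps the one outcome interviewer unaware of allocation at the randomised 8-week interview

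*Combined protocol and SAP*

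**What the plan says.** **Who runs the feedback interviews.** The paragraph after Table 3 in Section 6 lists the baseline, midpoint and final scale interviews together with the audio-recorded feedback interviews and gives both to one role: "semi-structured follow-up formative evaluation interviews with selected participants will be conducted by phone or videoconference by an interviewer trained and supervised by" a co-investigator. Section 15 (Risks) differs: "The participating investigators who would conduct the focus groups or semi-structured interviews are experienced in working with dementia caregivers". So does Section 18 (Privacy; numbered 19 in the table of contents): "The focus groups and semi-structured interviews will be conducted by study investigators, all of whom are experienced in interacting with caregivers". Sections 15 and 18 each describe the research interviewer separately from those investigators. Section 22 indicates that there is one interviewer, who is not an investigator: "This is a small study with only an interviewer and Center Program Manager involved beyond the investigators".

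**When they take place.** Section 10 says: "At the end point of each wave, we will purposively select 10 caregivers to participate in semi-structured interviews (total n=20". The payments paragraph of Section 13 says only that "about 20% will be asked to take part in semi-structured interviews following course completion".

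**How outcomes are collected.** Under Section 6, caregivers complete 30-minute phone or video interviews at baseline, at 8 weeks (after the immediate group's course and before the waitlist group enrols) and 8 weeks after that. Participants are randomised after baseline, and the waitlist half are told that they must wait. Table 3 lists scales of depression, anxiety, stress, burden, mastery and perceived competency, and reactions to care-recipient behaviours. Section 17 makes the randomised comparison the change from baseline to 8 weeks.

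**Masking.** No section says whether the interviewer is masked to allocation, who tells caregivers their arm, or who may see the Canvas course records.

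**The concern.** There are two problems, and they should be kept apart.

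The first is a plain contradiction. Three sections describe the staffing of the same 20 interviews, and they cannot all be followed. The answer decides whether the person who reads out the scales also discusses with caregivers what the course did for their sense of competence. Perceived competence is itself a Table 3 outcome.

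The second is a gap in the conduct of the randomised comparison. Caregivers cannot be masked, because they know whether they have been given the course. When subjective scales are administered by voice, an interviewer who knows the arm can differ in tone, prompting or probing between arms. That difference enters directly into the group-by-time effect at 8 weeks, which is the only contrast in the plan protected by randomisation. Keeping the interviewer unaware of allocation is the usual protection, and the plan neither provides it nor says that it is absent.

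**Working it through.** **1. The sections side by side**

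| Place | Who runs the feedback interviews |
|---|---|
| Section 6, after Table 3 | The trained and supervised interviewer, who also collects all scales |
| Section 15 | Investigators |
| Section 18 | Investigators |
| Section 22 | (Staffing) One interviewer, who is not an investigator |

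Two sections agree and one differs. Section 22 closes the possibility that the Section 6 interviewer is one of the investigators.

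**2. Could a feedback interview reveal allocation before the 8-week scales?**

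- Reach: 10 of 50 per wave, so 20 of 100 caregivers, or 20%.
- On Section 10's timing, read as after the wave's final interview, every feedback interview follows every scale interview in that wave. The number unmasked by this route before week 8 is 0.
- On Section 13's looser timing (after the course), a feedback call could precede the 8-week scales only for an immediate-arm caregiver who finished early and was called at once. Section 10 allows 6 to 8 weeks for the course.
- By the final scale interview both arms have been offered the course, so having taken it no longer identifies the arm.
- On the Section 17 calendar, wave 1 waitlist and wave 2 immediate both run over weeks 24-32. Wave 1 feedback could therefore coincide with wave 2's 8-week interviews, but it says nothing about who is in which arm of wave 2.

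One loose end remains. Section 13 places the follow-up interviews at 3 and 5 months, whereas Section 6 places them at 8 and 16 weeks. A lag between baseline and course start might explain this, but it leaves the order of feedback and scales unfixed.

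**3. Exposure that does not depend on the feedback interviews**

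At the 8-week call each caregiver knows their arm and can disclose it. Nothing withholds arm or course data from the interviewer. This exposure covers all caregivers interviewed at 8 weeks, whoever runs the feedback interviews.

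**4. Illustrative size**

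The plan gives no figure to reproduce on this point. From Section 17, n = 45 per arm and a 5% level. Assume that interviewer expectation shifts the mean change in one arm by δ SD of change when there is no true effect. Use a two-sample t-test with 88 degrees of freedom, two-sided critical value 1.987 and noncentrality δ × √(45/2) = δ × 4.743.

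| Assumed δ across the whole arm | Noncentrality | Rejection of a true null |
|---|---|---|
| 0.1 | 0.474 | 7.6% |
| 0.2 | 0.949 | 15.5% |
| 0.3 | 1.423 | 29.1% |

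These figures describe general interviewer bias. For the feedback interviews alone, take an extreme case that contradicts Section 10: all 20 are in the immediate arm and are held before week 8. The arm-average shift is then 20/50 of δ, that is 0.04, 0.08 or 0.12 SD, and rejection is 5.4%, 6.6% or 8.7%. On Section 10's timing, this route adds nothing and rejection stays at 5%.

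**The case against.** A reader might infer that Section 6 itself defeats masking: the outcome interviewer runs the feedback interviews, so the outcomes are collected by someone who has learned allocation. The documents do not support that link. Section 10 places the feedback interviews at the end of each wave, they reach one caregiver in five, and moving them to investigators would leave a caregiver just as free to disclose their arm in the 8-week call. The plan also makes no masking claim that could be defeated. This objection stands, and the point is worded accordingly.

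It can also be said that the 0.1 to 0.3 SD shifts have no source in the documents. That is correct; they are assumptions. Nor is a masked interviewer the only possible guard. Several of the instruments are self-report scales, and having caregivers complete them without an interviewer would also remove the interviewer's influence.

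Finally, this is a pilot seeking preliminary efficacy, and caregivers who know their arm may answer differently whoever asks. Masking the interviewer would not remove that second source of bias. These arguments limit how much the change can achieve. They do not resolve the contradiction among Sections 6, 15 and 18, and they do not explain why the plan is silent on the interviewer's knowledge of allocation at its only randomised contrast.

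**Conclusion.** Two things hold. Section 6 contradicts Sections 15 and 18 on who conducts the 20 feedback interviews. Separately, the plan does nothing to keep its single outcome interviewer unaware of allocation at 8 weeks, although the scales are subjective and interviewer-administered and caregivers know their arm. The first is not shown to cause the second.

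The size of any bias is unknown. The range of 7.6% to 29.1% false rejection rests on an assumed arm-wide shift of 0.1 to 0.3 SD with 45 per arm. It shows only that a small shift would matter in a trial of this size. This is an inexpensive improvement to the plan, not a flaw that invalidates the comparison.

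**What to change.** 1. Amend Section 6 to agree with Sections 15 and 18, so that investigators run the feedback interviews, and state in Sections 6, 10 and 13 that these follow the caregiver's final scale interview.
2. In Section 6, limit the research interviewer to the scripted scales, withhold arm and Canvas data from that person, and have someone else tell caregivers their group.
3. Open each follow-up call with a scripted line asking the caregiver not to mention the course or their group.
4. Have the interviewer record any unmasking at each call, and report the count by arm at 8 weeks.
5. If masking is judged unworkable, say so in Section 17 as a limitation of the 8-week comparison.

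The cost is wording in Sections 6, 10 and 13, one script line and one extra data field. Investigators give time to 20 interviews of about 45 minutes (20 × 45 = 900 minutes, or 15 hours), which Sections 15 and 18 already assign to them. No staff are added. The limit is that masking will sometimes break because caregivers know their arm, which is why unmasking should be recorded.
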